 1.1 If you indicated that personal identifiers will be maintained for future research, provide the following information: a) How the information will be securely handled and stored b) assure confidentiality, and c) who will have access to the identifiers and/or codes

2.0 Describe any additional steps, if any, to be taken to assure that the subjects' identities and any personal identifying information are kept confidential.

ID: IRB#14-001827

View: NEW 10.1 - Study Summary - Research Study

Warning: Save your work at least every 15 minutes by clicking &Save or &Continue.

Study Summary - Research Study -

1.0 Study Materials: As applicable to this study, attach the following:

- Protocol, Dissertation Proposal or Study Plan
- Preliminary Data
- Surveys, Questionnaires or other instruments to be used with study participants
- References

Document Name	Document Version #
LMIL Tables and Figures.docx	0.01
LMIL Bibliography and References cited.docx	0.01
Levomilnacipran proposal 042014.docx	0.01

2.0 *Specific Aims: Indicate the purpose of the research, specifying the problems and/or hypotheses to be addressed.

Specific Aims and Hypotheses:

Primary Aim: To compare the efficacy and generate estimates of the effect sizes on primary and secondary outcomes between the treatment groups in a 12 week double-blind placebo controlled treatment trial with levomilnacipran compared to placebo. Hypothesis 1: We will observe detectable differences in primary (mood) and secondary outcomes (cognition, apathy and quality of life) between the two treatment groups favoring LMIL.

Aim 2: To test whether the two treatment conditions will show no difference in tolerability and safety. We will particularly focus on cardiovascular status (blood pressure, heart rate, ECG changes)

Hypothesis 2: There will not be a difference in the rate of adverse events between the two groups.

Exploratory Aim 3: To compare the patterns of functional and structural connectivity in the two intervention groups. Hypothesis 3: LMIL will lead to improved functional connectivity in brain network activity as measured with resting state (rs-) fMRI, and plasticity in brain macro- and micro-structure as measured with structural MRI and DTI compared to the PBO.

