Imaging Biomarkers: Imaging data will be acquired from each subject at baseline and at 12-weeks post-randomization on a Siemens 3T Trio system using a 32-channel head coil. Each scanning session will last 60 minutes and include 1) a T1-weighted multi-echo MPRAGE (MEMPR) sequence with real time motion correction53 for the examination of brain structure and for use in network analyses; 2) a matched bandwidth T2 sequence for the detection and quantification of WMHs and CSF; 3) rs-fMRI to examine treatment related changes in functional activity at rest and intrinsic network connectivity; and 4) high angular resolution diffusion imaging (HARDI) to isolate changes in white matter microstructure and structural connectivity. Both rs-fMRI and diffusion imaging will utilize recently developed accelerated multiband pulse sequences with optimized spatial and temporal resolution (Table 3).54,55 Notably, the same multimodal imaging protocol has been implemented for a NIH study addressing biomarkers of geriatric depression in association with escitalopram both with and without augmentation of memantine treatment. In a separate extramurally funded project, we are also using this protocol to examine treatment effects and brain aging associated with Kundalini yoga. We are thus able to pool data and/or contrast results across studies as might be appropriate.

Resting State fMRI: During acquisition of blood-oxygen-level-dependent (BOLD) rs-fMRI data, subjects will remain awake with their eyes closed. Preprocessing will occur in a parallelized supercomputing environment using FSL56-58 and custom processing modules. Independent components analysis (ICA),59,60 will estimate the optimal number of components for each subject and time point and identify components representing artifacts. After low pass filtering (0.1-0.01 Hz) and transformation into atlas space, the best-fit default mode network (DMN) and executive and memory function network will be selected for each subject/time point for higher-level analysis. In follow-up analyses, seed regions-of-interest (ROIs) will be employed to examine voxel-level correlations between particular network nodes.60-62 In addition to subtracting changes between baseline and follow-

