up scans to determine associations with clinical response and neuropsychological function, we will represent fMRI maps as statistical change maps in time, with each voxel representing a smooth change in magnitude (positive or negative) from the baseline dataset. Notably, resting state activations are highly reproducible over time63 and experience-based neural plasticity in resting state connectivity has been shown over periods as short as 2-9 days.64 Recent research also shows significant changes in fronto-limbic connectivity in association with antidepressant treatment such as ECT65,66 as we have also shown [Fig. 3].

Diffusion Imaging: Diffusion data will be analyzed using FSL tools and include correction for slice prescription and residual eddy current distortions, tensor fitting, and tract based spatial statistics (TBSS)67 Changes in white matter FA, indicating fiber coherence and integrity, and radial, axial and mean diffusivity that point to changes in axonal structure and myelination, will then be examined across time and in relation to clinical outcome and neuropsychological function. Tractography methods will augment whole brain tract analysis and will be used to extract particular fronto-limbic fiber pathways using seed regions from both anatomical and functional imaging data. More sophisticated HARDI reconstruction techniques will be explored to determine more sensitive approaches for identifying changes in structural connectivity across treatment groups. Our previous data has shown increased FA and complementary decreases in mean and radial diffusivity in association with ECT and links with treatment-related clinical response that appear associated with processes of myelination (Lyden et al., 2014) [Fig. 4].

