experimental tests. Please describe the tests, provide a rationale for providing participants with the experimental test results and explain what, how and by whom participants and their health care provider will be told about the meaning, reliability, and applicability of the test results for health care decisions.

0

o 4.1.2

 Will tests be performed by a Clinical Laboratory Improvement Amendments (CLIA) approved lab?

o Yes No

5.0 *Indicate how much time will be required of the subjects, per visit or contact, and in total for the study.

This study will require that the participants make up to 10 visits in 12 weeks (three months) to the study site during their participation. Each participant will be required to commit approximately 10 hours in 3 months: visit 1 (2 hours); visit 2 (2 hours); visit 3-9 (each 30 minutes); visit 10 (2 hours).

6.0 *Statistics and Data Analysis: Describe the proposed statistical procedures or descriptive analyses for the study. If applicable, indicate how the sample size was determined.

DATA ANALYSIS. Data will be analyzed using the SAS (v9.3) statistical package. Data will be examined initially to identify issues such as departures from normality, which might suggest the need for transformation (e.g., logarithmic). Demographic variables (e.g., age, gender, etc.) and variables characterizing the course of depression (e.g., age of onset, chronicity, number of episodes, length of the current episode, etc.) will be compared by treatment group and examined in relation to outcome variables; this would define one possible set of appropriate covariates, if needed. Correlations (a) among outcome measures and (b) among potential covariates in the same domain will be examined to eliminate redundancy via possible data reduction, e.g., formation of composite scores or selection of single measures from sets of highly inter-correlated variables. Corrections for multiple significance testing will be performed within measurement domains when multiple measures are involved using Simes methods. Tests of the primary hypotheses that specify a predefined outcome measure will not be adjusted.

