Hypothesis 1: The primary analyses will focus upon HAM-D24 scores and will be analyzed using general linear mixed model analysis (e.g., SAS PROC MIXED). The two treatment groups will be compared for time course of HAM-D-24 with the initial endpoint EOT at 12 weeks. Covariates may be included in the model as noted above. In addition, likelihood ratio ?2 comparison will examine group differences in remission (HAM-D24 =6) and response (HAM-D24 =10) at EOT. Analyses for the cognitive outcome variables will be akin to those described above for the continuous HAM-D scores. As noted in the Neuropsychological Assessment section, there are four cognitive domains that are being assessed. Of these, the two primary cognitive domains of interest for this proposal are Cognitive Control and Episodic Memory. A separate general linear mixed model as above will be estimated using these two domain scores as dependent variables. The remaining domains, namely Verbal Fluency and Information Processing/Attention will be examined as secondary outcome measures. Apathy will be examined using the AES total score and quality of life using SF-36 scores in similar mixed models.

Hypothesis 2: We will examine adverse events in the two treatment groups. A detailed comparison of the number as well as type of side-effects in the two treatment groups will be conducted using chi-square tests.

Hypothesis 3: LMIL will lead to improved functional connectivity in brain network activity as measured with resting state (rs-) fMRI, and plasticity in brain macro- and micro-structure as measured with structural MRI and DTI compared to the PBO. To address these hypothesis, summary MRI measures (e.g., substructure volume, diffusion metrics) will be included in the GLMMs as "covariates of interest." For whole brain or structure voxel-level or point based measures (e.g., thickness or activation), the GLMMs will be implemented in R (www. R.org). Time (of scan) will be treated as a continuous variable with random intercepts and slopes to account for within-subject correlations between repeated measurements to assess change and interactions amongst the interventions. Difference scores between baseline and 12-week follow-up may be substituted for some analyses. FDR and/or permutation methods will be used to control for multiple anatomic comparisons in whole-brain contexts.

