Hypothesis 4: The role of brain neuroimaging biomarkers in variability of treatment response is examined in this Hypothesis. Predictor variables: We predict that baseline measures of neuroimaging biomarkers of emotional responsivity; working memory and connectivity will be related to treatment outcomes. These predictions will be evaluated in the context of the models described above (i.e., general linear mixed model) by adding the posited prognostic variable as an additional predictor.

Power. With a significance level (alpha) of 0.05, 80% power, and N = 30 in each treatment arm, we can detect an effect size (ES, difference between group means as a multiple of the standard deviation) of 0.7. Using appropriate covariates such as age of onset, chronicity, and number of episodes can be expected to reduce variance and increase power for a given difference in mean, hence the two-sample power computations are conservative for this situation. This study will thus yield sufficient pilot data to justify conducting a larger study in the future.

Data management. Data management and analysis support will be provided by the UCLA SI-STAT services and [name] will supervise the data gathering duties of the study coordinator, including reviewing all data entry forms. 1. Randomization. The prestudy forms must be submitted before a patient can be randomized. A separate portion of the database will also be maintained for patients screened but not enrolled or randomized. Randomization schedules will be prepared in a masked manner by the statistician. 2. Data submission and quality control. Data forms will be delivered from the originating location to the central data unit within one week of being generated. When errors, omissions, or unclear information is detected on the paper forms, a copy

will be returned for corrections. The data manager will generate monthly reports summarizing missing and incorrect data will be sent to the PI. 3. Data confidentiality. Patient study forms will be stored in locked file cabinets and will be accessible only to authorized personnel. A shredder will be used to discard all unwanted study documents. Access to the data will be password protected with only authorized persons having knowledge of the password.

ID: IRB#14-001827

View: NEW 11.1 - Characteristics of the Study Population

Warning: Save your work at least every 15 minutes by clicking \$Save\$ or \$Continue.

Characteristics of the Study Population

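### HARDI reconstructions are to be judged on sensitivity to change across treatment groups, with no arm-blinding and no correction for trying several; an added HARDI result picked that way would exceed its nominal error rate

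*Combined protocol and SAP*

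**What the plan says.** All references are to section 10.1 of the combined protocol and SAP.

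- **Named pipeline (item 4.0, Diffusion Imaging).** "Diffusion data will be analyzed using FSL tools and include correction for slice prescription and residual eddy current distortions, tensor fitting", followed by TBSS. The outputs are FA and radial, axial and mean diffusivity, with tractography of fronto-limbic pathways added.
- **Additional methods (same paragraph).** "More sophisticated HARDI reconstruction techniques will be explored to determine more sensitive approaches for identifying changes in structural connectivity across treatment groups". The methods are not named or counted. The text does not say which data will be used to judge them, whether the judging is blind to arm, or what is reported afterwards.
- **Status of the aim (item 2.0).** "Exploratory Aim 3: To compare the patterns of functional and structural connectivity in the two intervention groups". Hypothesis 3 under this aim predicts improved connectivity and structural plasticity on levomilnacipran relative to placebo.
- **Error control for Hypothesis 3 (item 6.0).** "FDR and/or permutation methods will be used to control for multiple anatomic comparisons in whole-brain contexts".
- **General multiplicity rule (item 6.0, Data Analysis).** "Corrections for multiple significance testing will be performed within measurement domains when multiple measures are involved using Simes methods".
- **Other data from the same scans (item 4.0, Imaging Biomarkers).** "Notably, the same multimodal imaging protocol has been implemented for a NIH study addressing biomarkers of geriatric depression". A second project, on Kundalini yoga, also uses this protocol, and the plan notes that data could be pooled or results contrasted across studies.

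**The concern.** A reconstruction can be called more sensitive only against a known signal. Whether the drug changes structural connectivity is the question under study, so a larger arm difference from one reconstruction does not show that it is the better method. If the drug has no effect, the reconstruction with the largest arm difference is the one with the most favourable noise. The only yardstick that the sentence gives is the contrast being tested.

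If that yardstick is applied to this trial's unblinded follow-up data and only the winning method is written up, its p-value no longer has its nominal meaning and its arm difference is biased away from zero. Neither multiplicity rule clearly prevents this. The FDR/permutation rule covers anatomic locations. The Simes rule covers multiple measures within a domain, and it cannot protect a result whose competitors were dropped before testing was reported.

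What is at stake is the credibility of one added imaging result in a pilot study whose findings are meant to justify a larger one.

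**Working it through.** **Is there a plan figure to reproduce?** No error rate, power or sample size is stated for Hypothesis 3. The 0.05 level comes from the general power statement in item 6.0 ("With a significance level (alpha) of 0.05, 80% power, and N = 30 in each treatment arm"), which is not specific to imaging. The calculation below therefore only sizes the problem on stated assumptions.

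**Inputs from the plan**
- Nominal level 0.05. Sidedness is not stated; two-sided is assumed.
- 60 randomised 1:1 with about 10% attrition, so 54 complete; 27 per arm if losses are even (item 4.0).

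**Assumed inputs**
- k = 3 or 5 reconstructions are tried on the arm contrast.
- Correlation between their test statistics is 0.5, 0.7 or 0.9, because they use the same scans.
- There is no true drug effect, and only the smallest p-value is reported, uncorrected.
- Each method gives a single scalar two-sample test. This is simpler than the voxel-level models in the plan.

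**Step 1: upper reference.** For independent methods, P(at least one p < 0.05) = 1 − 0.95^k.
- k = 3: 1 − 0.95³ = 0.143
- k = 5: 1 − 0.95⁵ = 0.226

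**Step 2: correlated methods.** Two-sample t tests were simulated at 27 per arm, with 200,000 null trials per setting. The table gives the proportion in which the smallest p-value is below 0.05.

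| Correlation | k = 3 | k = 5 |
|---|---|---|
| 0.5 | 12.6% | 18.4% |
| 0.7 | 11.0% | 15.0% |
| 0.9 | 8.3% | 10.3% |

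The range is about 8 to 18%, against 5% for one method fixed in advance. The more closely the methods agree, the smaller the inflation.

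**Step 3: exaggeration of the arm difference under no effect.** The standard error of a standardised difference is √(2/27) = 0.272. The mean absolute z is 0.80 for one fixed method. At correlation 0.7, the largest absolute z averages 1.18 for best of 3 and 1.34 for best of 5.
- One method: 0.80 × 0.272 = 0.22
- Best of 3: 1.18 × 0.272 = 0.32
- Best of 5: 1.34 × 0.272 = 0.36

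The 0.22 is ordinary sampling noise. Selection adds about 0.10 (best of 3) or 0.14 (best of 5).

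**Step 4: effect of the remedy.** One method fixed without arm information gives 5%. With Simes over all the methods tried, the simulated rate was 3.3% to 5.0% for k = 2, 3 and 5 and correlations from 0 to 0.9. Simes therefore controls the rate if every method is kept in the set.

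**The case against.** A reader might infer that the plan commits to ranking reconstructions on this trial's arm difference and then reporting the winner as the Hypothesis 3 result, so that the error rate of Hypothesis 3 as a whole is inflated. The documents do not support that, for these reasons.

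- **The selection rule is inferred.** Use of the trial's own data, and reporting only the best method, are natural readings of the sentence in its place, but neither is written. The sentence may describe the purpose of the work rather than a selection statistic. Same-protocol data from other studies exist, although the plan does not commit to using them for this choice.
- **A pipeline is already named.** Tensor fitting with TBSS stands, and nothing says that a HARDI method replaces it. At most, an added HARDI result is affected.
- **The aim is exploratory**, and the only error control stated specifically for Hypothesis 3 is over anatomic comparisons. Exploring methods is legitimate there if it is reported as such.
- **Simes might be read to apply**, if several reconstructions count as multiple measures in one domain.
- **Nothing ties a diffusion effect size to the design of the larger study.** Item 2.0 links effect-size estimation to the primary and secondary outcomes, and the power paragraph says only that the pilot data would justify a larger study.

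All of this limits the point, and the first four items are why its size is conditional. It does not remove the point. The only criterion written down is still the treatment contrast, and no passage requires arm-blinding, a separate data set or correction over methods. Simes helps only if all the methods tried are carried into it.

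It is also fair that fixing the HARDI choice leaves other imaging choices open. For example, "Difference scores between baseline and 12-week follow-up may be substituted for some analyses". The remedy is not a guarantee of 5% for the whole imaging programme.

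**Conclusion.** The point holds in a conditional and limited form. The plan names sensitivity to change across treatment groups as the basis for judging HARDI reconstructions and gives no safeguard against choosing on the outcome. If the choice is made on this trial's arm difference and only the best method is reported, that HARDI result would carry a false-positive rate of about 8 to 18% instead of 5%, with an exaggerated arm difference. The size rests on the assumed 3 to 5 methods, correlations of 0.5 to 0.9, a two-sided test and a scalar summary per method; the plan gives none of these.

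The tensor and TBSS results and the primary HAM-D analysis are untouched. This is an inexpensive improvement to an exploratory part of the plan, not a threat to the trial's main conclusion.

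**What to change.** Replace the HARDI sentence in item 4.0 with a rule along these lines:

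1. The HARDI reconstruction is chosen without arm information, on this trial's baseline scans or on the other studies that use the same imaging protocol.
2. The criterion is one that does not involve the treatment contrast, such as goodness of fit or reproducibility.
3. The choice is documented and fixed before unblinding.
4. The arm comparison from that reconstruction is reported beside the named TBSS measures and labelled exploratory.
5. If several reconstructions are run on the arm contrast, all are reported, with either a permutation null for the maximum statistic over reconstructions or Simes over the full set of methods tried.

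The cost is a short change to the imaging text and some computing. No further scans or visits are needed. The downside is that the method fixed in advance may not be the one that shows the largest arm difference.

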The rationale for the duration of the interventions, follow up, and blinding procedures: The proposed study is of standard duration for the geriatric population requiring 12 weeks or longer trials to document antidepressant efficacy.

4.0 *Research Design and Methods: Describe in detail the design and methodology of the study.

Subjects: We anticipate screening about 100 subjects to recruit 60 older depressed adults (>60 y.o.) who will be randomized to receive 20-120 mg of levomilnacipran blindly with increment dose titration 20 mg per day -3 days; 40 mg per day-3 days. Based on efficacy and tolerability, we will increase by 40 mg per day each following week 2nd-4th week the maximum recommended doses is 120 mg per day. The comparison group will receive similar blinded titration with matching placebo. Doses of the drugs will be adjusted according to individual tolerability and safety. We expect an attrition rate of about 10% based on our prior experience thus 54 subjects will complete the study. Patients will be assessed pre-treatment; and then weekly during the first four weeks and bi-weekly thereafter. At all visits, clinical ratings of mood, vital signs, and safety will be obtained. Inclusion criteria: 1) The presence of a major depressive disorder diagnosed according to the DSM-IV criteria. 2) A 24-item Hamilton Rating Scale for Depression (HAMD) score of 17 or higher at baseline. 3) Mini-Mental State Exam (MMSE) score > 24.

Exclusion criteria: subjects will be excluded if they had 1) any current and/or lifetime history of other psychiatric disorders (except unipolar depression with or without comorbid generalized anxiety disorder), or 2) recent unstable medical or neurological disorders; 3) any disabilities preventing their participation in the study or in the MRI; 4) diagnosis of dementia; 5) acute suicidality; 6) those with known allergic reactions to milnacipran, uncontrolled narrow angle glaucoma, seizures, poorly-controlled hypertension or ischemic changes on ECG, serotonin syndrome, or the recently used MAOIs within last 4 weeks; 7) ineligible for MRI (e.g., metal in the body or claustrophobia)

Primary outcome will be measured and defined as follows: 1) Remission will be defined as HAMD scores of 6 or less for three consecutive weeks and at week 12; 2) Improvement in depression severity using HAMD scores.

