Measures of medical comorbidity (administered at baseline and at week 12 or upon early termination): Stroke Risk Factor Prediction Chart (SRF)38,39 of the American Heart Association for rating cerebrovascular risk factors (5 min). Cumulative Illness Rating Scale-Geriatric (CIRS-G),40 used for rating the severity of chronic medical illness in 14 organ-systems (15 min). Health-Related Quality of Life and Physical functioning ((administered at baseline and at week 12 or upon early termination): Medical Outcomes Study Short Form 36-Item Health Survey (SF-36)41, an instrument that measures health-related quality-of-life, mental, physical, and social functioning (15 min). The Connor-Davidson Resilience scale (CD-RISC), as a measure of stress coping ability42 (5 min); the Quality of Life Enjoyment Scale (Q-LESS-Q),43 a brief assessment instrument of life satisfaction, which has been commonly used in the clinical trials in psychiatric populations including the elderly (5 min). We have included a self-reported physical activity record for monitoring physical activity in both groups (3 min).44

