Randomization and treatment schedule: After all screening and baseline test results are reviewed and eligibility criteria are confirmed, medications will be dispensed if patients continue to meet eligibility criteria and sign the informed consent form. All eligible subjects will be randomized to levomilnacipran or placebo group using a computer-generated random assignment scheme, which assigned subjects in a 1:1 ratio to each group. Randomization will be done prior to subject s being assigned to the groups.

Follow up assessment: The follow up will take place weekly for the first four weeks of treatment, every two weeks for the remainder of the study. Each follow up assessment will include measures of efficacy and safety. The weekly frequency of contact with all subjects will serve as an additional safeguard to monitor worsening of depression, as well as the emergence of side-effects or suicidal ideations.

Study medications and treatment procedures. Subjects will be randomized to: 1) LMIL20-120 mg per day or 2) matching placebo. The allowed range of the drugs according to tolerability and efficacy assessments will be between 20-120 mg per day for LMILN. The dose finding procedures will be only performed in the first four weeks and after that will remain stable until the end of the acute trial, as it worked in our pilot study. We will assess the optimal dose of LMIL based on tolerability and safety in this population. The balance will be maintained between the efficacy and tolerability of medications. If symptoms worsen, the study drug will be tapered and discontinued. Subjects will be referred for clinical care at UCLA or the community. The PI will continue the observation for safety until the appointment is scheduled with the primary psychiatrist. The dose will be titrated according to the titration schedule, including if side-effects are mild or well tolerated and if CGI scores for improvement is 3 or higher. The titration rate is based on the currently recommended titration to achieve the greatest efficacy that may not work for geriatric patients. For that reason, we have safeguards against rapid titration with potential side-effects that will require a slower titration or staying at a lower dose.

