Network Connectivity: Based on observations that brain regions are interconnected and that these connectivity patterns exhibit certain regularity as well as randomness associated with small world networks, we will use graph theory-based methods to determine whether changes in network connectivity reflect plasticity associated with treatment response. Specifically, diffusion and anatomical data will be used to capture features such as local clustering (between cortical ROIs obtained from the structural analyses described above) combined with long-distance connections between clusters (white matter tracts) [Fig. 6].77-82 Connectivity metrics will include overall strength, coherence, and efficiency in local networks and globally across the entire brain.

WM Hyperintensities (WMH). The 3D T2-space images will be used to visualize WMHs by employing a semi-automated WMH identifier.83 Briefly, WMH burden will be assessed based on the signal intensities of co-registered 3D MEMPR and T2 images, and population statistics on the spatial distribution and neighborhood structure of WM lesions. GLM and multiple regression analyses will determine links between WM burden, clinical measures and vascular risk factors in each group, which may be controlled for other analyses.

The drug placebo differences in geriatric depression are minimal within 5% of each other averaging about 30-40% each. Because we are addressing neural mechanisms of antidepressant response, placebo-controlled study will help evaluate this better than another active comparator. We are skilled in monitoring risks and side-effects of drugs, including emerging and worsening symptoms of depression and suicidality.

Depression and Suicidality.

We will include the Columbia Suicide Rating Scale as a supplemental measure of suicidality and worsening of depression. The measure is designed to include all suicide-relevant variables as well as other risk and protective factors to assist the study doctor in weighing these factors for determining overall risk.

- 4.1
- * Will you be providing results of any experimental tests that are performed for the study?

,	
	Yes - Complete Items 4.1.1 and 4.1.2
	No
	Not Applicable

- o 4.1.
 - You indicated in Item 4.1 that the research involves

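### White-matter lesion links are planned by group, with no time point and no lesion-by-arm test; one model across both arms would be more precise and harder to misread

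*Combined protocol and SAP*

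**What the plan says.** The paragraph on WM hyperintensities in section 10.1, item 4.0, states that "GLM and multiple regression analyses will determine links between WM burden, clinical measures and vascular risk factors in each group", and adds "which may be controlled for other analyses". It does not say whether two models or one model with group terms is meant, or which scan or visit supplies the data.

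The time point matters because every ingredient is measured more than once. Under Imaging Biomarkers, "Imaging data will be acquired from each subject at baseline and at 12-weeks post-randomization". The stroke risk chart, used "for rating cerebrovascular risk factors", is completed at baseline and at week 12 or early termination. The HAM-D is taken at all visits.

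None of the hypothesis tests in item 6.0 names lesion burden. The Hypothesis 3 models mention interactions in general terms. The Hypothesis 4 model adds the imaging marker as one more predictor and states no marker-by-treatment term.

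**The concern.** Two uses of these regressions need different handling, and fitting by arm suits neither.

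- **Baseline links.** Before any drug is given, the arms are random halves of one sample. The true relation between lesion burden, vascular risk and baseline severity is therefore the same in both, and any difference between arms is chance. Splitting halves the sample and gains nothing.
- **Links with week-12 outcomes.** Here the relation could truly differ by arm, because one arm has been treated. Two separate slopes, each with its own p-value, do not test that difference. One significant slope and one non-significant slope is a common result even when the true slopes are equal.

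At stake are precision that the data could already supply, and the chance that a one-arm finding in a 60-person pilot is taken as evidence that lesion burden changes the drug's effect. Because these factors may also be adjusted for elsewhere and no time point is fixed, adjustment for a week-12 value is not ruled out.

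**Working it through.** **Inputs.** Item 6.0 (Power) gives "With a significance level (alpha) of 0.05, 80% power, and N = 30 in each treatment arm". Allocation is by a scheme "which assigned subjects in a 1:1 ratio to each group". On dropout, item 4.0 says "We expect an attrition rate of about 10% based on our prior experience thus 54 subjects will complete the study", which is 27 per arm if losses are equal. Sidedness is not stated; two-sided is assumed. The true correlation r is not in the documents; 0.2 to 0.5, equal in both arms, is assumed.

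**The plan's own figure.** The plan says "we can detect an effect size (ES, difference between group means as a multiple of the standard deviation) of 0.7". The detectable difference is (1.960 + 0.842) × √(2/30) = 0.723, or 0.736 with the t distribution. Both round to 0.7. The figure concerns a difference in means; the plan gives no power figure for the lesion analysis.

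**Precision, split against pooled.** With Fisher's z = artanh(r) and SE = 1/√(n − 3), the detectable r at 80% power is tanh(2.802/√(n − 3)).

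| n in the fit | SE of z | Detectable r | 95% CI if observed r = 0.30 |
|---|---|---|---|
| 30 (one arm) | 0.192 | 0.49 | −0.07 to 0.60 |
| 60 (both arms) | 0.132 | 0.355 | 0.05 to 0.51 |
| 27 (one arm, completers) | 0.204 | 0.52 | −0.09 to 0.61 |
| 54 (both arms, completers) | 0.140 | 0.37 | 0.04 to 0.53 |

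The arm term costs one degree of freedom: at 60, tanh(2.802/√56) = 0.358.

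**Power and one-arm significance.** Per-arm power p is Φ(artanh(r)√(n − 3) − 1.960) plus the negligible opposite tail; the pooled fit uses √(n − 4). The chance of significance in exactly one arm is 2p(1 − p). Example at r = 0.30, n = 30: artanh(0.30) = 0.3095, × √27 = 1.608, so p = 36.3% and 2 × 0.363 × 0.637 = 46%.

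| Shared true r | Power per arm, n = 30 | Power pooled, n = 60 | Exactly one arm, n = 30 each | Exactly one arm, n = 27 each |
|---|---|---|---|---|
| 0 | 5% | 5% | 9.5% | 9.5% |
| 0.2 | 18% | 33% | 30% | 28% |
| 0.3 | 36% | 64% | 46% | 44% |
| 0.35 | 48% | 78% | 50% | 49% |
| 0.4 | 60% | 89% | 48% | 50% |
| 0.5 | 81% | 98% | 30% | 36% |

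A simulation with 20,000 replicates at r = 0.2, 0.3, 0.4 and 0.5 agreed with these figures to within about two points. A single slope-by-arm test in the same simulated data declared a difference in 4.7% to 5.2% of trials.

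**What the interaction test can find.** The difference in Fisher z detectable with 80% power is 2.802 × √(2/27) = 0.76 at 30 per arm, for example r = 0 against tanh(0.76) = 0.64. At 27 per arm it is 2.802 × √(2/24) = 0.81, or r = 0 against 0.67.

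**The case against.** The strongest reply is that the sentence says less than a critic needs it to say.

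- A reader might infer that two separate models are definitely planned. That is the natural reading, but the wording also fits one model with group-specific slopes. This objection stands; the sentence needs settling either way.
- A reader might infer that the analysis is confined to baseline, so that any split is wasteful. The text sets no such limit. Week-12 links can truly differ by arm, and Exploratory Aim 4 is partly about whether imaging markers modify improvement. By-arm slopes are reasonable description there.
- A reader might infer that significance in one arm only will be presented as a drug effect. No comparison of these links between arms is announced, so this is a hazard of the format, not a stated analysis.
- A reader might infer that the by-arm results will select covariates. The phrase about control is permissive and may simply name lesion burden or vascular risk as optional covariates. No selection rule is given.
- Quoting only r between 0.30 and 0.40 would put one-arm significance at 44% to 50%, but that range sits near the maximum of 2p(1 − p). The wider range is fairer, and the calculation treats a simple correlation where the plan has multiple regression.

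The interaction test is also weak at this size. These replies narrow the point and lower its importance. They do not supply a reason to split a baseline relation by arm, and they do not point to any lesion-by-arm test elsewhere in the plan.

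**Conclusion.** The point holds as a cheap improvement of minor severity. On the natural reading, baseline links would be estimated with about 30 people instead of 60, raising the detectable correlation from 0.355 to 0.49. For week-12 links, the plan has no test of whether arms differ. Under an equal true correlation of 0.2 to 0.5, separate fits would show significance in exactly one arm in about 28% to 50% of trials.

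The precision figures rest on the planned arm sizes and a two-sided 5% level. The 28% to 50% range rests also on the assumed correlations, for which the documents give no value. The analysis is exploratory. It does not alter the sample size, and it reaches the primary HAM-D comparison only if lesion burden is added there as a covariate.

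**What to change.** Revise the sentence in the WM hyperintensities paragraph to state:

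1. **Baseline links:** one regression on all randomised participants with a baseline scan, with arm as a factor.
2. **Week-12 clinical outcomes:** one model with baseline lesion burden, arm and their interaction. Any statement that the arms differ rests on the interaction term with its confidence interval; by-arm slopes are descriptive only.
3. **Use in other models:** where lesion burden or vascular risk is adjusted for, the baseline value is used.

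The cost is a few lines of text, with no new data or visits, and by-arm slopes remain available from the same model. The limitation to state alongside is the low power of the interaction test: a non-significant result will not show that the arms share the same link.
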